### 3) Background

Breast cancer is a disease with high incidence that will affect the life of one of every eight women in the United States. Early detection of breast cancer is the most important factor determining prognosis, and X-ray mammography is the principal screening tool for breast cancer world-wide. While mammography is not without shortcomings, it nevertheless plays an important and documented role in reducing mortality associated with breast cancer. The principal weakness of mammography is in its application to women with extremely dense, glandular breasts. Imaging the dense breast with good sensitivity has taken on more importance as younger women (40-49 year age group) are now screened routinely, as the use of hormone replacement therapy has expanded, and as genetic testing identifies younger women at risk. Equalization techniques have been shown to increase the effective dynamic range of mammography, however their technical complexity has hampered widespread adoption. Digital radiographic systems, finally nearing wide-scale clinical use, have the promise of improving mammography of the dense breast due to their increased dynamic range over screen-film mammography. However, like screen-film mammography, digital mammography integrates all anatomical structures in the breast onto a planar projection image. The fundamental problem of detecting breast cancer in dense breasts is the superposition of multiple overlaying glandular structures, which can obscure the visualization of a breast tumor. A fundamental solution to this problem lies in the use of tomographic imaging techniques, which vastly reduces

anatomical complexity by separating overlapping structures into individual tomographic images of the breast.

### Summary of Initial Experience

Dedicated breast computed tomography (bCT) is a fully tomographic cone beam x-ray based imaging modality that generates three dimensional images of the breast. In initial clinical trials, bCT was shown to provide significantly better visualization of mass lesions than that capable with mammography; however mammography outperformed bCT in visualizing microcalcifications.[1] Further work using injected iodine based contrast medium in conjunction with bCT, or so called contrast-enhanced bCT (CE-bCT), verified that mass lesions are seen better on CE-bCT than on mammography. However, the visualization of microcalcifications, specifically those associated with a malignant lesion, was similar at CE-bCT and mammography, suggesting that the use of iodine contrast medium may close the gap between bCT and mammography in visualizing malignancy.[2] Due to the contrast injection, CE-bCT is a more invasive procedure than mammography and may not be appropriate as a modality for breast cancer screening in the general population. CE-bCT may have more potential as a tool for screening in high risk patients, for cancer staging, and for tumor targeting. Unenhanced bCT may still serve as an important imaging modality for tumor staging and targeting in patients with contraindications to iodine contrast imaging.

### Contrast Enhanced Breast CT Significance

Contrast injections are used to identify breast cancer lesions in clinical procedures, most notably breast MRI (gadolinium contrast agent). Other investigators have demonstrated the utility of iodine contrast agent injection for breast cancer delineation in projection mammography techniques, using both dual energy subtraction (Lewin) and temporal subtraction (Yaffe) to highlight the visualization of the breast tumor.

#### 4) Inclusion and Exclusion Criteria

##### Inclusion Criteria:

- Age at least 35 years old
- Diagnostic findings from prior mammography highly suggestive of breast malignancy (BI-RADS® category 4 or BI-RADS® category 5)
- Not pregnant or breast-feeding
- Ability to lay still and hold breath for approximately 15 seconds

##### Exclusion Criteria:

- Recent breast biopsy
- History of moderate or severe reaction to contrast agent injection (these subjects can still participate in the non-contrast CT scanning)
- History of Allergy to Iodine
- History of multiple food and/or drug allergy
- Currently taking Glucophage or Glucovance (Metformin)
- History of Chronic Asthma
- History of Diabetes Mellitus
- Renal (kidney) disease, or solitary kidney
- Recent lab tests showing elevated serum creatinine ( $\geq 1.5$  mg/dL)
- Recent lab tests showing estimated glomerular filtration rate (eGFR)  $\leq 60$  ml/minute
- Positive urine pregnancy test or currently breast-feeding
- Inability to understand the risks and benefits of the study
- The standard MRI contraindications apply, including but not limited to: having a pacemaker or other implanted electronic device, metal foreign bodies within the eye, aneurysm clips, heart valve prosthesis, vascular stents, coils, intrauterine devices (IUDs), inferior vena cava (IVC) filters, gunshot wounds with retained bullet fragments. (MRI only)
- Prisoners

Subject candidates will be informed of the study's existence when they are told that they need a biopsy. Posters will also advertise the clinical trial, and the posters will be placed in the scan rooms and consultation areas. Brochures will also be available in the mammography facility (Suite 0500 ACC). Mammography staff including technologists, clinical coordinators, fellows, or radiologists will inform the patient of the clinical trial. If the patient expresses an interest, a mammography technologist or study coordinator will review their eligibility and obtain contact information for a subsequent phone call. Patients may also be given a brochure by the scheduler, at the time of scheduling their biopsy. Patients who have expressed an interest or who have taken a brochure will be called by the

study coordinator, who will use a script. If the candidate agrees to participate, the coordinator will schedule the MRI scan and breast CT scans.

**5) Study Timelines**

The duration of the subject's active participation is approximately 1.5 hours.

The duration of the subject's pathology follow-up is ~2-3 months.

The estimated date to complete the study is approximately December 31, 2022.

**6) Study Endpoints**

**Primary:** The primary study endpoint will be the assessment of patient safety and comfort at the conclusion of the imaging phase of the study.

**Secondary:** The secondary study endpoint will be the comparison of breast MRI versus breast CT in terms of sensitivity and specificity using biopsy findings as the standard of truth for lesion characterization. True positives & negatives and false positive & negatives will be defined and ROC (receiver operating characteristics) curves will be generated.

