### Contrast Injection Procedures

(Note: If the study subject cannot tolerate iodinated contrast, or IV placement is not possible, the subject may still participate in the non-contrast CT scanning.)

After aseptically prepping the patient's skin, a intravenous catheter will be inserted into the antecubital vein. The patient will be positioned in the scanner as described above and the IV will be connected to the power injector. 100 ml of contrast agent (Omnipaque-350 350 mg I/ml) at a rate of 4ml/sec will be injected over the course of approximately 25 seconds. In the event the subject has bilateral breast lesions, the contrast administration will be split into two separate injections. 50 ml of contrast at 4ml/sec will be injected prior to scanning the first breast, and a second 50 ml at 4ml/sec will be injected prior to imaging the second breast. The total radiation dose will be the same as that for those subjects who receive the single 100 ml contrast injection. Post-contrast CT scanning will begin approximately 90 seconds after the start of injection. This time point represents the expected peak concentration of contrast in the circulation. Total time for this visit is approximately 45 minutes.

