**11) Withdrawal of Subjects**

A subject will be considered to have successfully completed their participation in the study at the conclusion of the scanning procedure. If a subject is removed or withdraws from the study, the specific reasons for discontinuation will be clearly documented in the subject's study file.

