**12) Risks to Subjects**

This study involves a small amount of radiation exposure that is typical of other diagnostic tests involving the use of radiation exposure (such as a mammogram).

The amount of radiation exposure received in this study is below the levels that are thought to result in a significant risk of harmful effects.

Risks associated with iodine-based IV contrast injection are as follows:

Minor/Common risks:

- Bruising/infection at the IV site
- Nausea & vomiting
- Urticaria
- Pruritis
- Diaphoresis

Severe/Rare risks:

- Pulmonary edema
- Respiratory arrest
- Cardiac arrest
- Seizures

Moderate/Uncommon risks:

- Faintness
- Facial edema
- Laryngeal edema
- Bronchospasm

Risks associated with gadolinium-based IV contrast injection are as follows:

Minor/Common risks:

- Bruising/infection at the IV site

Severe/Rare risks:

- Nephrogenic Systemic Fibrosis (NSF)

Risks associated with MRI scans are as follows:

Minor/Common risks:

- Claustrophobia

Special IV Contrast Patient Safety Precautions:

A doctor will be present during each contrast-enhanced breast CT and MRI scan to monitor the subject for signs and symptoms of adverse reaction to the contrast injection. A fully-stocked hospital-issued crash kit will be available for emergency treatment. Emergency Medical Services (EMS) will be called for immediate transport to the UCDMC emergency department. Verbal and written post contrast instructions will be provided to the patient at the end of the study visit.

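### The primary safety endpoint is timed to the end of imaging, with no planned search for later adverse events, so the adverse event rate may be understated

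*Combined protocol and SAP*

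**What the plan says.** Section 6 sets the primary endpoint and its timing: "The primary study endpoint will be the assessment of patient safety and comfort at the conclusion of the imaging phase of the study". It does not list the events that count or give a collection window.

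Section 11 says: "A subject will be considered to have successfully completed their participation in the study at the conclusion of the scanning procedure". Section 5 puts the time involved at about an hour and a half ("The duration of the subject's active participation is approximately 1.5 hours") and adds, separately, "The duration of the subject's pathology follow-up is ~2-3 months".

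Section 7 gives each woman one questionnaire about her experience once the scans are done. It notes that her medical record may still be consulted afterwards for follow-up information, without saying what for or for how long.

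Safety observation is on site. Section 10 requires technologists and a physician to be present during scanning, and Section 12 has a doctor present for each contrast scan. Section 10 also sets out adverse event reporting to the IRB, with a five-day limit for serious, unanticipated and related events and annual review for the others. It has no cut-off at the end of scanning.

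Section 12 lists "Bruising/infection at the IV site" among the minor or common risks, once for the iodine agent and once for the gadolinium agent.

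**The concern.** The assessment time in Section 6 does not fit the risk list in Section 12. IV-site infection is named as a common risk of both injections, yet the observation the protocol arranges ends when the woman leaves the scanner. An infection that develops at home would enter the primary result only if somebody happened to report it.

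What is at stake is the meaning of a favourable result. A finding of few or no events could be read as covering the risk of the contrast injections as a whole, when active observation covered only what could be seen on site. Unascertained events can only lower the count, so any error runs towards a more favourable safety profile.

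**Working it through.** **1. Length of the on-site window.** Section 7 gives the same duration for the breast CT visit and the breast MRI visit: "Total time for this visit is approximately 45 minutes". Then 45 + 45 = 90 minutes = 1.5 hours, which reproduces the active participation time in Section 5. That figure therefore contains no allowance for a later safety contact.

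**2. What is planned after the window.**

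| Element | Section | Looks for later adverse events? |
|---|---|---|
| Questionnaire after the scans | 7 | No; completed once, about the experience |
| Staff or physician presence | 10, 12 | No; during scanning only |
| IRB reporting | 10 | No; handles events that become known, with no cut-off |
| Pathology follow-up, about 2-3 months | 5 | Not stated; labelled as pathology |
| Continued record access | 7 | Possible, but purpose not stated |

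No section schedules a post-visit call, an adverse event check of the record, or a collection window for the endpoint.

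**3. What a zero result would establish.** The documents give no event rate, precision target or power for safety. The planned 400 women in Section 8 come from the AUC calculations. With 0 events in n women, the one-sided exact 95% upper bound is 1 - 0.05^(1/n), and the two-sided exact limit is 1 - 0.025^(1/n).

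- n = 400: 1 - 0.05^(1/400) = 0.75% one-sided; 1 - 0.025^(1/400) = 0.92% two-sided.
- These bounds apply only to events that the study would have ascertained. Later, unsought events are not bounded.
- 400 is also not the number exposed to contrast. Section 7 lets women take part with non-contrast CT only, or without MRI. The exposed numbers are not given. If 300 or 200 women received an agent (assumed), the one-sided bound would be 1 - 0.05^(1/300) = 0.99% or 1 - 0.05^(1/200) = 1.49%.

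**4. Direction of the error.** Let p be the true event rate and f the share of events that arise after the visit and never come to light. Neither is in the documents. The expected observed count is n × p × (1 - f), which cannot exceed n × p, and the chance of observing none is [1 - p(1 - f)]^n. Taking n = 400 and p = 1% purely for illustration, that chance is 0.99^400 = 1.8% at f = 0, 0.995^400 = 13.5% at f = 0.5, and 0.999^400 = 67% at f = 0.9. This shows which way the result moves and is no estimate for this trial.

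**The case against.** The strongest reply is that Section 10 reports adverse events with no end date and Section 8 keeps the reports, so later harms are not shut out. That is correct. A reader might infer that the endpoint is blind to anything after the visit, and the documents do not support that. But Section 10 deals with events already known. It does not plan to find them, and it is not linked to the endpoint.

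Second, the imaging phase in Section 6 may be that of the whole study. Section 8 describes four years of recruitment, so on this reading most women would have months or years in which events could surface. The wording is ambiguous. Sections 7 and 11 favour the per-woman reading. On the study-level reading there is still no planned search, and women scanned last would have little follow-up.

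Third, Section 7 allows CT and MRI on different days, with the biopsy appointment after both. A second visit might reveal a problem from the first injection. It does nothing for the second injection, and both scans may fall on the day of biopsy.

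Fourth, a reader might add nephrogenic systemic fibrosis or renal events as harms that the window must miss. The documents give no onset time for the former, so neither the present window nor a 2-3 month one can be judged against it. Renal events are not in the Section 12 risk list, and Section 4 excludes renal disease and raised creatinine. The content of the post-contrast instructions is not given, so they prove nothing about expected timing. IV-site infection is the example that stands.

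**Conclusion.** The point holds as a gap in planned ascertainment and in the definition of the endpoint. The protocol times its primary safety assessment to the end of imaging, lists a common harm that would not be expected to show by then, and arranges no inquiry afterwards.

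The adverse event rate may be understated. That it will be is a stronger reading the documents do not support, since they give no event rate and no late share, and late events may still surface through Section 10. No percentage can be attached to the shortfall, because any such figure would only restate an assumed late share.

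The conclusion rests on two judgements: that an infection from an IV line would rarely be visible within a 45-minute visit (the documents give no onset time), and that Section 6 is meant per woman. If the study-level reading is intended, the gap is smaller for women scanned early, but the lack of planned ascertainment remains. The correction is worthwhile and inexpensive, and it does not bear on the AUC comparisons.

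**What to change.** In Section 6, define the safety endpoint per woman as all adverse events from the first study scan or injection through the existing pathology follow-up at about 2-3 months. State that comfort alone is assessed at the end of imaging.

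When the record is opened for pathology, abstract contrast reactions, IV-site complications and unplanned visits onto the case report form. Section 7 already foresees record access, but its purpose should now be stated, because no section describes a record review for safety.

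Report on-site and later events separately. For each contrast agent, use the women who actually received it as the denominator, and label any confidence bound as one-sided or two-sided.

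The cost is a few extra form fields. Care received elsewhere will be captured incompletely, so the later-event rate should be presented with that limit. The reported event rate may also be higher than under the present plan.

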**7) Procedures Involved**

The patient's biopsy appointment typically occurs about 1 week after her diagnostic work-up in the Mammography clinic. Breast CT and breast MRI scans may take place on different days, or both may be done on the day of her biopsy appointment. Whichever is done first will depend on the clinical MRI clinic schedule. The second scan, whether it is breast CT or breast MRI, will take place prior to the subject's scheduled breast biopsy appointment.

**Breast CT:**

The subjects will arrive at the Ambulatory Care Center, Suite 0500 on the day of their study breast CT. The woman to be scanned will lie prone on a large table (which is covered by a foam pad), and she will place the breast to be scanned in a small hole in that tabletop. The hole is surrounded by a soft neoprene "hammock," which will allow the woman's entire upper torso to slump into the scan plane of the device. After positioning of the breast by a female mammography technologist, two single projection scout images will be acquired to confirm proper positioning and two additional single projection images will be acquired with a tungsten collimator placed at the X-ray tube for scatter correction. The woman will be instructed to hold her breath (for approximately 15 seconds) and the scan will commence. There will be no breast compression (as in mammography), and other

than the sound of the relatively noisy x-ray system in the room, the woman will not feel or sense any aspect of this scan.

### Contrast Injection Procedures

(Note: If the study subject cannot tolerate iodinated contrast, or IV placement is not possible, the subject may still participate in the non-contrast CT scanning.)

After aseptically prepping the patient's skin, a intravenous catheter will be inserted into the antecubital vein. The patient will be positioned in the scanner as described above and the IV will be connected to the power injector. 100 ml of contrast agent (Omnipaque-350 350 mg I/ml) at a rate of 4ml/sec will be injected over the course of approximately 25 seconds. In the event the subject has bilateral breast lesions, the contrast administration will be split into two separate injections. 50 ml of contrast at 4ml/sec will be injected prior to scanning the first breast, and a second 50 ml at 4ml/sec will be injected prior to imaging the second breast. The total radiation dose will be the same as that for those subjects who receive the single 100 ml contrast injection. Post-contrast CT scanning will begin approximately 90 seconds after the start of injection. This time point represents the expected peak concentration of contrast in the circulation. Total time for this visit is approximately 45 minutes.

### Breast MRI:

The subjects will arrive at the Ambulatory Care Center, Suite 0500 on the day of their study breast MRI. After screening by an MRI technologist for MRI contraindications, an I.V. will be placed in the subject's forearm. The subject will then be positioned on the scan table prone, with each breast hanging into separate holes of the MRI coil. Pre-contrast scanning will then take place (short T-1 inversion recovery (STIR) and T-1 weighted pulse sequences). MRI contrast will then be injected (Omniscan (Gadodiamide) GE Healthcare) at a dose of 0.2 ml/kg and at a rate of 2 ml/second by a power injector. 15-20 ml of normal saline will be used as a flush. Post-contrast scanning will then take place. Following this, the subject's visit will be complete. Total time for this visit is approximately 45 minutes.

**NOTE:** If a subject wishes to participate, but cannot or will not, undergo MRI scanning, the subject may still be enrolled for the CT portion only.

After the scans have finished, the participant will be given a questionnaire to complete about their experience during the study. After completion of the scans and completing the questionnaire, their active participation in the study will be

completed. Access to their medical record for follow up information may continue.

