Numbers of patients needed: To size the studies, we have conducted power analyses [Abbey et al., 2013] based on the Roe and Metz simulation (2,000 runs) for a fixed effects ANOVA model instead of the usual mixed effects model proposed by Dorfman, Berbaum, and Metz (DBM) or correlated error model of Obuchowski and Rockette (Hillis SL, et al., 2005). For the normal-risk bCT-screening study (Aim 4), we have sized the study on the basis of 4 readers, an improvement of 0.05 in AUC, and with average AUC near 0.85 (i.e. AUC = 0.825 vs AUC = 0.875). At these performance benchmarks, 82% power is achieved with 150 positive cases and 250 negative cases. This is a reasonable number of cases given the recruitment procedures described in §D3.1. For the CE-bCT/CE-MRI (high risk screening) comparison (Aim 5), we investigate the non-inferiority of breast CT relative to MRI. We will consider breast CT to be successful in the pilot study if the observed difference in reader-averaged AUC values is greater than -0.025 (i.e.  $AUC(BCT) - AUC(MRI) > -0.025$ ), for a study in which average AUC is approximately 0.85. The Roe and Metz simulation [Abbey, et al, 2013] with 4 readers and 150 cases (60 positive and 90 negative) yields 82% power for finding non-inferiority as defined above in 2,000 independent simulation runs. We expect to be able to recruit at least this many patients for this study based on the recruitment procedures described above.

Informed consent and subject accountability:

There will be a clear accounting of all subjects involved with the study. This includes subjects who are consented, screened, eligible and enrolled as well as ineligible subjects. If a candidate is deemed ineligible for enrollment, the reason for ineligibility will be recorded. There will also be a listing of all patients discontinued or withdrawn from the study after enrollment. These statistics will be reported to the IRB during annual reviews when required.

All subjects participating in this study will provide written consent in the form of the Informed Consent Form. The investigators will allow the candidate to read the consent form and will ask the candidate if they have any questions prior to enrollment. Subject initials, signatures, and date and time will be required in the appropriate places on the form.

Data Handling and Data Management:

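### Comfort, half of the primary endpoint, is asked about only after the scans have finished, with no provision for women who stop a scan early; a summary of the questionnaire would tend to overstate comfort

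*Combined protocol and SAP*

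**What the plan says.** Section 6 defines the endpoint: "The primary study endpoint will be the assessment of patient safety and comfort at the conclusion of the imaging phase of the study". It gives no scale, threshold, summary measure or analysis set for comfort.

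Section 7, under Breast MRI, describes the one self-report instrument: "After the scans have finished, the participant will be given a questionnaire to complete about their experience during the study". The next sentence, which begins "After completion of the scans and completing the questionnaire, their active participation in the study will be", puts the end of active participation after both the scans and the form. Section 7 also allows CT and MRI on different days, in either order, and lets a woman who cannot or will not have MRI enrol for CT alone.

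Section 11 defines completion: "A subject will be considered to have successfully completed their participation in the study at the conclusion of the scanning procedure". For a woman who is removed or withdraws, it requires that "the specific reasons for discontinuation will be clearly documented in the subject's study file". Section 8 adds: "There will also be a listing of all patients discontinued or withdrawn from the study after enrollment". Section 8 also says that data from all subjects enter the safety and efficacy evaluation; it does not mention comfort. Section 12 lists "Claustrophobia" among the minor or common MRI risks, and nausea and vomiting among the minor or common risks of iodinated contrast.

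**The concern.** Stopping a scan can itself be the comfort outcome. A woman who leaves the MRI because of claustrophobia, or ends a CT session because she feels unwell after contrast, has told the investigators something important about tolerability. The stated trigger for the questionnaire is that the scans have finished, so she is the woman least likely to have a score. Whether a score is missing would then depend on the quantity being measured. A larger sample does not reduce that bias.

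A second group is easy to overlook. The trigger refers to scans in the plural, and the two scans may be on different days. A woman who completes breast CT and later stops MRI may never reach the trigger, so her rating of the CT, the device under study, may go uncollected for a reason unrelated to CT.

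At stake is the credibility of a favourable comfort result in the primary endpoint. A reader could not tell whether it describes all women scanned or only those who got through.

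**Working it through.** **Step 1. Who reaches the questionnaire if the text is followed as written?**

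| Course | Provision for a comfort score |
|---|---|
| Completes CT and MRI | Yes (Section 7) |
| Enrolled for CT only, completes CT | Yes, on a natural reading: all her scans have finished |
| Stops during her first scan | None stated; reason for discontinuation filed (Section 11) and woman listed (Section 8) |
| Completes CT, starts MRI, stops | None stated; the CT-only note covers women who do not undergo MRI, not an MRI begun and abandoned |

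The all-subjects sentence in Section 8 does not fill the last two rows, because it cannot supply a score that was never collected. The discontinuation reasons could help, but no section links them to the comfort endpoint.

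**Step 2. The plan's own number.** The only sample size that could apply to comfort is the recruitment minimum in Section 8: 150 / 0.38 = 394.7, given there as 395 and rounded to 400. It reproduces. It comes from the cancers needed for the reader study; no comfort rate, threshold or power is stated.

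**Step 3. Size of the possible overstatement.** Let p be the favourable share among completers, d the share of women who stop without a questionnaire, and q the favourable share those women would have reported.

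- All-women rate = p(1 − d) + qd
- Overstatement if only questionnaires are summarised = p − [p(1 − d) + qd] = d(p − q)

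The documents give none of p, d or q. All three below are assumptions, as is the split into favourable and unfavourable. With N = 400 and p = 0.95:

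| d (women) | All-women rate, q = 0 | Overstatement, q = 0 | Overstatement, q = 0.5 | 95% half-width among completers |
|---|---|---|---|---|
| 2% (8) | 0.95 × 0.98 = 93.1% | 1.9 points | 0.9 | 2.16 |
| 5% (20) | 0.95 × 0.95 = 90.25% | 4.75 points | 2.25 | 2.19 |
| 10% (40) | 0.95 × 0.90 = 85.5% | 9.5 points | 4.5 | 2.25 |

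The half-width is 1.96 × √[p(1 − p) / (400(1 − d))].

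**Step 4. Sensitivity to p.** With q = 0 and d = 5%, the overstatement is 4.0 points at p = 0.80 (half-width 4.02) and 4.5 points at p = 0.90 (half-width 3.02). At p = 0.90 and d = 1% to 2% it is 0.9 to 1.8 points, below the half-width of about 3 points. It is zero when d = 0 or q = p.

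So in the worst case (q = 0) the bias is below sampling error when about 2% or fewer stop. At 5% it is about equal to sampling error if p = 0.80 and larger if p is 0.90 or 0.95.

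**The case against.** The strongest reply is that the protocol never restricts comfort to completers. A reader might infer that the primary endpoint is scored on completers and that women who stop contribute nothing. The documents do not support that: no comfort analysis set is defined, the one general statement on analysis refers to all subjects, and reasons for discontinuation must be recorded and the women listed. Nor does the protocol name the questionnaire as the sole source for comfort, or bar use of those records. The trigger can also be read loosely: scanning that ended early has, in a sense, finished. The questionnaire is not in the text I read, so any instruction printed on it is unknown.

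Several features also limit the problem. Entry requires a woman to be able to lie still and hold her breath for about 15 seconds. CT uses no compression. Women who cannot tolerate iodinated contrast may have the non-contrast scan. Claustrophobia is listed for MRI, not CT. Contrast reactions should be captured as adverse events under Section 10, and so in the safety half of the endpoint. No hypothesis or sample size rests on comfort.

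Most of this stands, and it rules out saying that comfort will be overstated by a known amount. It does not close the gap. Two consecutive sentences in Section 7 place the form after the scans, and the second speaks of their completion, so the literal reading is the likelier one in practice. A recorded reason for stopping is not a comfort rating unless the plan says how it is used.

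**Conclusion.** The point holds as a gap in how a primary endpoint is collected. The one described comfort instrument is tied to finished scans, and no rule covers a woman who stops early or who finishes CT but stops MRI. Followed literally, such women have no questionnaire score, and a summary of the questionnaire would tend to overstate comfort.

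The direction rests on stoppers being less comfortable than completers, which is reasonable when the reason for stopping is intolerance. The size is not known. The range of 1.9 to 9.5 points assumes 2% to 10% stopping, 95% of completers favourable and every stopper unfavourable. It roughly halves if half the stoppers would have been favourable. A stronger claim, that the plan builds in a bias of that size, would go beyond the documents.

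The change is worth making because the endpoint is primary and the remedy is nearly free.

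**What to change.** In Sections 6 and 7:

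- Give the existing questionnaire at the end of each scan attempt, CT and MRI separately, whether the scan was completed or stopped early.
- Report comfort for all women in whom a scan was started, stating how many have a questionnaire and how many do not.
- Report beside the scores, for each modality, the proportion who stopped for intolerance, taken from the discontinuation reasons (Section 11) and the listing of discontinued women (Section 8).
- Add a sensitivity analysis that counts intolerance stops as unfavourable. This is one defensible choice among several, so it belongs beside the main summary and should not replace it.

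This needs a few sentences, no new instrument and no change to clinical management. The cost is slightly more form handling, including a second form for women who have both scans, and a comfort figure that may be slightly less favourable.
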